Dosage of the drugs: Ivermectin 6 mg 2 tab stat, cap Doxycycline 100 mg 1 cap BD 5 days

Content of the placebo:

Placebo description of Ivermectin: Attached with Annexure 1

Product Name: Placebo Tablet of Ivec 6 Tablet

Batch No.: PB029

Mfg. Date: JUN 2020

Exp. Date: MAY 2022

Appearance: A pale yellow colored, round, standard bi-convex uncoated tablet with a bre line on one side and other side plain

Composition:

SL. No.	MATERIAL NAME	QUANTITY PER TABLET	PERCENTAGE PER TABLET
1.	Microcrystalline Cellulose (PH102)	63.355 mg	74.544 %
2.	Pregelatinised Starch (Starch 1000)	20.000 mg	16.500 %
3.	Sodium Starch Glycolate (Type A)	9.375 mg	7.500 %
4.	Anhydrous Citric Acid	0.013 mg	0.010 %
5.	Butylated Hydroxyanisol (BHA)	0.012 mg	0.010 %
6.	Pigment Blend Yellow PB0071	0.045 mg	0.036 %
7.	Colloidal Anhydrous Silica (Aerosil 200)	0.500 mg	0.400 %
8.	Magnesium Stearate	1.750 mg	1.400 %

Placebo Description of Doxycycline: Attached with Annexure II

Product Name: Placebo Capsule of Doxibac 100 Capsule

Batch No.: PB030

Mfg. Date: JUN 2020

Exp. Date: MAY 2023

Appearance: Hard gelatin capsule shell size #2 having white opaque body imprinted with popular logo in black ink and dark blue opaque cap containing white granular powder

Composition:

SL. No.	MATERIAL NAME	QUANTITY PER CAPSULE	PERCENTAGE PER CAPSULE
1.	Anhydrous Lactose	247.650 mg	88.440%
2.	Microcrystalline Cellulose (PH102)	7.350 mg	2.626%
3.	Sodium Starch Glycolate (Type A)	20.000 mg	7.143%
4.	Magnesium Stearate	5.000 mg	1.766%
5.	EHGC Shell Size #2 (Body: White Opaque, Cap: Dark Blue Opaque)	1 Pc.	---

Estimated study date: 01 June, 2020

Estimated primary completion date, 25 August 2020

Estimated study completion date: September, 2020

Inclusion Criteria:

- At least 18 years of age
- COVID-19 infection, confirmed by polymerase chain reaction (PCR) test within 3 days from enrollment
- Only mild and moderate COVID-19 infected cases
- Able to provide informed consent

Exclusion Criteria:

- Unable to take oral medication
- Pregnant or breast feeding lady
- Patients with severe COVID symptoms or admission in ICU/HDU

- Alanine Aminotransferase (ALT) or aspartate aminotransferase (AST) > 5 X upper limit of normal (ULN)
- On non-invasive positive pressure ventilation or mechanical ventilation at time of study entry
- Known hypersensitivity to Doxycycline or ivermectin or its components.

Research instruments:

1. Informed consent form.
2. Case record form

Primary Outcome Measure:

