The number of days required for clinical improvement

1. Early Clinical improvement of the patients
How many days it requires to become the patient completely symptoms free
[Time Frame: 7 days]
2. Late clinical recovery
How many days the symptoms persist
[Time Frame: 12 days]

Secondary Outcome Measure:

1. Percentage of patients having clinical deterioration.
Patients deteriorating to next level of severity, like moderate, severe and death
[Time Frame: 1 month]
2. Persistently positive for RT-PCR.
Percentage of Covid-19 Patients repeatedly become positive for RT-PCR for Covid-19
[Time Frame: 14 days]

Data collection technique:

Data will be collected by assigned. trained data collectors (Physician).

Patient will be enrolled according to defined inclusion and exclusion criteria in the current research. Informed written consent will be obtained from the patient or their relatives. Each patient participating in the trial will be uniquely identified, and information such as his name, address is recorded in the trial 'subject number list'. Only the principle investigator will be aware about the allocation of the drugs. The patients

and the data collectors will be unaware about the group allocation of the drugs. The Data will be reviewed by the co-investigators. It will be managed by principle and co-principle investigators in designated computer.

Clinical assessment (fever, cough, Anorexia, Temperature, pulse, blood pressure, respiratory rate, oxygen saturation) will be done every day. Routine investigation (CBC, ESR, CRP, Creatinine, RBS, SGPT, chest x-ray, D- Dimer) will be done at admission and at day 3, 5, 7, 10 and 14 day. In case of the clinical deterioration it would done according to necessity. RT-PCR will be done at day-0, Day 5, day 7 and day 14.

Standard care: both the experimental and placebo will receive the available standard of care, like-

- Paracetamol, Antihistamine, Cough suppressant, Vitamins
- Oxygen therapy according to indication and need
- Low molecular weight heparin according to indication
- Appropriate other broad spectrum antibiotics
- Other drugs for associated co- morbid condition

Management of the adverse events:

Drugs adverse effect will be monitored by a defined committee. The patient experiencing adverse effect of the drugs will be discontinued from the study. It will be managed with priority to the highest possible level by the hospital authority as well as the investigators.

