These patients usually present with symptoms of an upper respiratory tract viral infection, including mild fever, cough (dry), sore throat, nasal congestion, malaise, headache, muscle pain, or malaise. Signs and symptoms of a more serious disease, such as dyspnea, are not present.

Moderate Pneumonia

Respiratory symptoms such as cough and shortness of breath (or tachypnea in children) are present without signs of severe pneumonia.

Severe Pneumonia

Fever is associated with severe dyspnea, respiratory distress, tachypnea (> 30 breaths/min), and hypoxia ($\text{SpO}_2 < 90\%$ on room air). However, the fever symptom must be interpreted carefully as even in severe forms of the disease, it can be moderate or even absent. Cyanosis can occur in children. In this definition, the diagnosis is clinical, and radiologic imaging is used for excluding complications.

Acute Respiratory Distress Syndrome (ARDS)

The diagnosis requires clinical and ventilatory criteria. This syndrome is suggestive of a serious new-onset respiratory failure or for worsening of an already identified respiratory picture. Different forms of ARDS are distinguished based on the degree of hypoxia. The reference parameter is the $\text{PaO}_2/\text{FiO}_2$:

- Mild ARDS: $200 \text{ mmHg} < \text{PaO}_2/\text{FiO}_2 \leq 300 \text{ mmHg}$. In not-ventilated patients or in those managed through non-invasive ventilation (NIV) by using positive end-expiratory pressure (PEEP) or a continuous positive airway pressure (CPAP) $\geq 5 \text{ cmH}_2\text{O}$.
- Moderate ARDS: $100 \text{ mmHg} < \text{PaO}_2/\text{FiO}_2 \leq 200 \text{ mmHg}$.
- Severe ARDS: $\text{PaO}_2/\text{FiO}_2 \leq 100 \text{ mmHg}$.

When PaO_2 is not available, a ratio $\text{SpO}_2/\text{FiO}_2 \leq 315$ is suggestive of ARDS.

Chest imaging utilized includes chest radiograph, CT scan, or lung ultrasound demonstrating bilateral opacities (lung infiltrates $> 50\%$), not fully explained by effusions, lobar, or lung collapse.

Clinical improvement Criteria

1. Body temperature remains normal for at least 3 days (ear temperature is lower than 37.5°C).

2. Respiratory symptoms are significantly improved.
3. Lung imaging shows obvious improvement in lesions.
4. There is no co-morbidities or complications which require hospitalization.
5. SpO₂, >93% without assisted oxygen inhalation.

8. FLOW CHART of Study workup:

Sl No	Activities						
		1 st	2 nd	3 rd	4 th	5 th , 6 th , 7 th	8 th

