Clinical Feature

Trait			Follow-up Yes-1, No-2												
	On Enrollment		D 2	D3	D4	D-5	D-6	D-7	D-8	D-9	D-10	D-11	D-12	D-13	D-14
Fever	 Yes	 No													
Cough	 Yes	 No													
Running nose	 Yes	 No													
Sputum	 Yes	 No													
Respiratory distress	 Yes	 No													
Sore throat	 Yes	 No													
Hoarseness of voice	 Yes	 No													
Chest pain	 Yes	 No													
Diarrhoea	 Yes	 No													
Vomiting	 Yes	 No													
Anosmia	 Yes	 No													
Anorexia	 Yes	 No													
Headache	 Yes	 No													
Confusion	 Yes	 No													

Obsrvation

Trait		Follow-up Yes-1, No-2												
	On Enrollment	D 2	D3	D4	D-5	D-6	D-7	D-8	D-9	D- 10	D- 11	D- 12	D- 13	D- 14
Temperature														
Pulse rate														
BP														
Respiratory Rate														
Oxygen saturation														
Co- Morbidity	DM/HTN/ IHD/ HF/ CKD/CLD/Asthma/COPD/Malignancy/ CTD													

Investigations Profile

Trait	Value					
	Admission	D-3	D-5	D-7	D-10	D-14
Hb						
WBC						
Neutrophil						
Lymphocyte						
Platelet						
ESR						
CRP						
RBS						
Creatinine						
SGPT						
D-Dimer						
Na						
K						
ECG						
Covid-19 RT-PCR						

Radio-Imaging

Trait	Findings
Chest X-Ray CT Chest	Normal/ Consolidation (unilateral or bilateral) / Patchy opacity Consolidation/ Ground Glass Opacity/nodule/ multifocal

Principal Investigators:

Date:

Annexure-1

Popular Pharmaceuticals Ltd.

QUALITY ASSURANCE DEPARTMENT

Certificate of Analysis

Product Name: Placebo Tablet of Imec 6 Tablet

Batch No.: PB029

Mfg. Date: JUN 2020

Exp. Date: MAY 2022

Appearance: A pale yellow colored, round, standard bi-convex uncoated tablet with a break line on one side and other side plain

Composition:

SL. No.	MATERIAL NAME	QUANTITY PER TABLET	PERCENTAGE PER TABLET

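### Malaise and muscle pain, which the protocol names as features of mild illness, are recorded nowhere in the daily data, so the symptom-free date in the primary outcome can fall too early

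*Protocol*

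**What the plan says.** Under Primary Outcome Measure the early component is "How many days it requires to become the patient completely symptoms free", with a 7-day time frame. The late component is "How many days the symptoms persist", with a 12-day time frame. Neither component names the symptoms that count.

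Three places in the protocol list symptoms:

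- Data collection technique: "Clinical assessment (fever, cough, Anorexia, Temperature, pulse, blood pressure, respiratory rate, oxygen saturation) will be done every day".
- Case Record Form, Clinical Feature table: 14 yes/no rows, completed at enrolment and on each of days 2 to 14. They range from fever and cough to less prominent items such as "Hoarseness of voice".
- Operational definition, Uncomplicated (mild) Illness: upper respiratory symptoms "including mild fever, cough (dry), sore throat, nasal congestion, malaise, headache, muscle pain, or malaise".

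The third list matters because the Inclusion Criteria admit "Only mild and moderate COVID-19 infected cases". The Clinical improvement Criteria, also under the operational definitions, set a different standard for symptoms: "Respiratory symptoms are significantly improved", alongside conditions on temperature, imaging, complications and oxygen saturation.

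**The concern.** An outcome that requires every symptom to have gone can be dated only from records that cover the symptoms patients are expected to have. The protocol expects its mild patients to have malaise and muscle pain, among other symptoms, yet gives the data collector no place to record whether either is present on a given day.

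Two errors can follow. If one of these symptoms outlasts every recorded one, the last recorded symptom sets the recovery date, and that date is too early. If they are a patient's only symptoms, every row reads No at enrolment, and the form cannot tell that patient from someone with no symptoms.

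Neither error can be repaired at analysis, because the data were never collected. For that reason it cannot be left to a statistical analysis plan. There is also a lesser problem: the text and the form give symptom lists of different length, and nothing says which one decides when a patient is symptom free.

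**Working it through.** No figure in the plan bears on this point, so the check is a comparison of lists. The one calculated figure, 121 per group under Methodology, does not depend on the symptom lists. As printed, ½ × [(1.96 + 0.845) / (arcsin√0.40 − arcsin√0.58)]² = 120.05, which rounds up to 121. Nothing below changes it.

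**Step 1: count the distinct symptoms.** The text list has 3 (fever, cough, anorexia), leaving aside its 5 vital signs. The form has 14. The mild-illness description has 7, counting malaise once although it is printed twice.

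**Step 2: trace the 7 mild-illness symptoms.**

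| Symptom | Text list | Form grid |
|---|---|---|
| Fever | yes | yes |
| Cough | yes | yes |
| Headache | no | yes |
| Sore throat | no | yes |
| Nasal congestion | no | not by name; the Running nose row is close |
| Muscle pain | no | no |
| Malaise | no | no |

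The text list omits 7 − 2 = 5 of the 7. The form omits 7 − 4 = 3 by name, or 2 if Running nose is taken to cover nasal congestion. The firm omissions are malaise and muscle pain, which are on neither list. Only fever and cough appear on all three lists.

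**Step 3: compare the text with the form.** All 3 text symptoms are rows on the form, and 14 − 3 = 11 form symptoms are not in the text. The text list is a strict subset of the form.

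**Step 4: what this does to the event date.** Let R be the first day on which every recorded symptom is absent, and U the first day on which malaise and muscle pain are both absent. The outcome as worded is the later of R and U. The form can supply only R. The two agree when U ≤ R. When U > R, the recorded date is early by U − R days. A patient with no recorded symptom at enrolment has R at enrolment, whatever U is.

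**Step 5: direction.** Suppose a fraction f of the patients in each arm who are still symptomatic at some time point is scored as recovered. True recovered proportions p₁ and p₂ become p₁ + f(1 − p₁) and p₂ + f(1 − p₂). Their difference becomes (1 − f)(p₁ − p₂), which is smaller than the true one. This holds only if f is the same in both arms. The documents give no value for f, so none is inserted.

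**The case against.** The case for leaving the plan alone has several parts.

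- **The form is a named research instrument, and the text list sits wholly inside it.** Nothing tells a data collector to stop at three symptoms. This stands. A reader might infer from 3 against 14 that eleven symptoms go unrecorded. The documents do not support that: a completed form captures all 14, and what remains is doubt about which list governs.
- **The outcome wording is itself strict.** A patient with muscle pain is not free of symptoms, and trained physicians see patients daily. This is fair as a reading of the words. But the form has no row in which the physician's observation could be kept, so the date cannot be derived or verified from the record.
- **The mild-illness text is an open-ended severity description, not an endpoint list.** This also stands, and the two lists need not match item for item. It is nevertheless the protocol's own statement of how these patients usually present, and the outcome demands freedom from all symptoms.
- **Running nose largely covers nasal congestion.** Accepted. That item needs only a clearer label.
- **No bias between arms is shown.** Accepted. The protocol keeps patients and data collectors unaware of allocation.
- **A larger conflict lies between being free of all symptoms and the Clinical improvement Criteria.** That conflict is real, and extra rows alone would not settle it. The definition and the criteria therefore need to be reconciled at the same time.

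**Conclusion.** The point holds as a modest measurement defect in the primary outcome. Two symptoms that the protocol attributes to mild patients are recorded nowhere in the daily data, so the symptom-free date can fall too early and a patient with only those symptoms can appear recovered at enrolment.

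Its size is 2 of the 7 mild-illness symptoms missing from both lists. The number of patients affected is unknown, because the documents do not say how often malaise or muscle pain outlasts the other symptoms or occurs alone.

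A reader might go further and conclude that the primary outcome is wrongly dated in general, or that a stated number of percentage points is lost from the treatment difference. The documents support neither. The date is wrong only when U exceeds R, and any percentage would be invented.

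That the error dilutes the difference, and does not favour one arm, is an expectation resting on two assumptions. The first is that blinded data collectors complete the form alike in both arms. The second is that premature scoring affects the same share of still-symptomatic patients in each arm. Blinding supports the first and does not guarantee the second.

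**What to change.** Make these changes before enrolment, since symptom data not collected cannot be recovered:

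1. Add daily rows for malaise and muscle pain to the Clinical Feature grid, and label the Running nose row to include nasal congestion.
2. Under Data collection technique, replace the short symptom list with a statement that all symptoms on the grid are assessed every day, together with the vital signs already named.
3. Under Primary Outcome Measure, define the symptom-free day as the first day on which every grid row designated for the primary outcome is marked No, and use the same rows for the late component. Mark the designated rows on the form, so that whether a symptom such as anosmia counts is settled in advance.
4. Reconcile this definition with the Clinical improvement Criteria, and state which of the two the primary outcome uses.

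The cost is two extra tick-box rows per day on a form already completed daily. Over the 14 columns (enrolment and days 2 to 14) that is 2 × 14 = 28 additional ticks per patient, plus a few sentences in the protocol. The sample size calculation is unaffected.

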Covid-19 is an emergent pandemic, threatens the life of millions of the people throughout the globe. There is increasing effort of the scientist to unveil a remedy of covid-19. Still it is unsuccessful. At present there is no other alternative other than experimenting the existent drug against the virus. There are several trials going throughout the globe. Among them Ivermectin showed good efficacy in vitro trial. Some clinical trial also proved it beneficial. The Doxycycline also has some anti-viral role with its prominent anti-inflammatory role. Synergistic action of the two drugs might be proved some benefit in clinical trial. As both drugs are cheap and less toxic, if it does, it would be the blessing for the poor people of the globe.

4. METHODOLOGY:

Study type: Interventional Clinical trial

Estimated enrollment: 200 participants per group

For superior trial, the formula is:

$$N = \frac{1}{2} \times \left(\frac{Z_{\frac{\alpha}{2}} + Z_{\beta}}{\arcsin \sqrt{p} - \arcsin \sqrt{P_0}} \right)^2$$

N=size per group; p=the response rate of standard treatment group; p₀= the response rate of new drug treatment group; z_x= the standard normal deviate for a one or two sided x; d=

the real difference between two treatment effect; δ_0 = a clinically acceptable margin; S^2 = Pooled standard deviation of both comparison groups.

All parameters were assumed as follows: $p = 0.40$; $p_0 = 0.58$; $\alpha = 0.05$; $\beta = 0.20$; $\delta = 0.18$; $\delta_0 = 0.10$.

$$N_{\text{statistical superiority}} = \frac{1}{2} \times \left(\frac{1.96 + 0.845}{\arcsin \sqrt{0.40} - \arcsin \sqrt{0.58}} \right)^2 = 121$$

However, we are assuming that lost to follow up or refuse to include in trial will be 20%, that means 24. So at least 150 patients will be allocated randomly and power of this study will be 80%.

Allocation:

Randomized: Block randomization (Computer generated randomization code)

Intervention model: Parallel assignment

Intervention model description: Patient will be randomized 1:1 to placebo with standard care and combined doxycycline and ivermectin with standard care.

Blinding: Double blind (The participant and the clinicians/data collectors will be unaware of the treatment the participant receives)

Primary purpose: Treatment

Official title: A phase III trial to promote recovery from covid 19 with combined Doxycycline and Ivermectin along standard care.

Provider of placebo and active ingredients: Popular pharmaceutical limited

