If the patient progresses from mild to moderate or severe disease, the study will be continued and available management of the appropriate severity will be immediately started. The patient will be monitored closely.

Data analysis:

Data will be analyzed by computer with the help of SPSS (Statistical Package for Social Sciences) version 20. To compare mean of the two group chi square will be used. Comparing drug outcome in between two group survival analysis by Kaplan-Meier curve will be done for the duration of recovery. Odds ratio will be formulated from linear logistic regression for early and late clinical recovery. Hazard ratio will be formulated from the cox regression analysis for severity conversion and persistence of the positivity. Crude odds ratio will be adjusted in cox proportional hazard ratio model. Each Ivermectin-Doxycycline plus standard of care group will be compared with the placebo plus standard care group using the log-rank test, hazard ratio and 95% CI. Participants who were lost to follow up, died, discontinue drugs due to adverse effect will censored on the last study day. All P values will be two-sided and will be shown without

adjustment for multiple testing. All analyses will be performed according to the intention to treat principle.

Dropout management: Intention to treat measure will be taken

Observation and Results:

Result of the study and statistical analysis will be presented by tables, figures, graphs, diagrams, charts and photographs. All these would have own legends (i.e. title) and will be serially numbered.

Discussion:

Discussion will be done on the basis of result obtained from the study and comparing with similar studies done at home and abroad.

Summary:

Summarization will be drawn after discussion.

Conclusion:

Conclusion would be drawn depending upon the results and discussion

Conflict of interest:

Popular pharmaceutical will only provide drugs and the placebo.
None of the investigators will receive remuneration from the pharmaceutical company.
They will not get any access to data profile.

Operational definition:

(According to WHO guideline)

Confirmed Covid-19:

Cases with positive RT-PCR for Covid 19 irrespective of symptoms.

Uncomplicated (mild) Illness

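### Logistic odds ratios for day-7 and day-12 recovery cannot use the patients whom the same paragraph censors, so these results can be distorted if loss differs by arm

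*Protocol*

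**What the plan says.** All references are to the Protocol, section 4 (Methodology).

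- *Primary Outcome Measure* lists early clinical improvement (time frame 7 days) and late clinical recovery (time frame 12 days), both worded as numbers of days.
- *Data analysis* gives these two outcomes a binary analysis: "Odds ratio will be formulated from linear logistic regression for early and late clinical recovery". A logistic model needs a yes/no status, which I read as recovered by day 7 and recovered by day 12.
- The same paragraph plans that "survival analysis by Kaplan-Meier curve will be done for the duration of recovery", and that the active group is "compared with the placebo plus standard care group using the log-rank test, hazard ratio and 95% CI".
- It then sets one rule for three kinds of incomplete patient: "Participants who were lost to follow up, died, discontinue drugs due to adverse effect will censored on the last study day".
- It closes by placing all analyses under intention to treat. The next line reads "Dropout management: Intention to treat measure will be taken".
- The sample-size text states: "However, we are assuming that lost to follow up or refuse to include in trial will be 20%, that means 24".
- *Management of the adverse events* states: "The patient experiencing adverse effect of the drugs will be discontinued from the study".

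**The concern.** The methods fixed in one paragraph do not fit together. A patient who leaves on day 4 without having recovered is censored under the stated rule, but a logistic model for recovery by day 7 has no such category. Leaving the patient out conflicts with intention to treat. Counting the patient as not recovered assigns an outcome nobody observed. The two choices can push the odds ratio in opposite directions, and the protocol does not choose between them.

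The censoring rule does not settle the matter, because its last day can be read two ways. If it is the patient's last day seen, a patient who died is treated as someone who could still have recovered. If it is the end of the study, a patient lost on day 4 is treated as watched to the end without recovering.

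Loss may also be unequal, since patients with an adverse drug effect leave the study and this could happen more often on active treatment. The day-7 and day-12 results would then partly reflect who left rather than who recovered.

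**Working it through.** **1. The plan's own figure.** With the stated formula and rates 0.40 and 0.58:

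N = 0.5 × [(1.96 + 0.845) / (arcsin√0.40 − arcsin√0.58)]² = 0.5 × (2.805 / 0.1810)² = 120.05, rounded up to 121 as stated. I therefore use 0.40 (placebo) and 0.58 (active), with the planned 200 per group. The protocol does not tie these rates to a day; taking them as day-7 rates is my assumption.

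True day-7 odds ratio: (0.58/0.42) / (0.40/0.60) = 2.07.

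**2. Further assumptions, none of them in the protocol.** Daily recovery has a constant hazard. Loss is unrelated to recovery within each arm. The last day seen is spread evenly over days 0 to 6.

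**3. Share of lost patients who have not recovered when they leave.** This is the mean of (1 − p)^(c/7) over c = 0 to 6, which equals p / {7 × [1 − (1 − p)^(1/7)]}.

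- Placebo: 0.40 / (7 × 0.07038) = 0.812, so 0.188 recover before leaving.
- Active: 0.58 / (7 × 0.11656) = 0.711, so 0.289 recover before leaving.

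**4. Day-7 proportions for a loss fraction L.**

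- Lost counted as not recovered: (1 − L)p + L × (share recovered before leaving).
- Unknown status dropped: the same numerator divided by 1 − L × (share not recovered on leaving).

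Worked case, 10% placebo and 30% active:

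- Placebo 0.9 × 0.40 + 0.1 × 0.188 = 0.379; active 0.7 × 0.58 + 0.3 × 0.289 = 0.493; odds ratio 1.59.
- Dropped: 0.379 / (1 − 0.081) = 0.412; 0.493 / (1 − 0.213) = 0.626; odds ratio 2.39.

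| Loss placebo/active | Lost = not recovered | OR | Unknown status dropped | OR |
|---|---|---|---|---|
| 20% / 20% | 0.358 / 0.522 | 1.96 | 0.427 / 0.608 | 2.08 |
| 15% / 25% | 0.368 / 0.507 | 1.77 | 0.419 / 0.617 | 2.23 |
| 10% / 30% | 0.379 / 0.493 | 1.59 | 0.412 / 0.626 | 2.39 |

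Simulation agrees: about 1.94 to 1.95 and 2.06 to 2.07 for equal loss, and 1.59 and 2.40 for 10%/30%. Kaplan-Meier with censoring at last contact recovers the true 2.07 under these assumptions.

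**5. Tests at 200 per group, 10%/30% loss (simulation).** Power is about 61% with lost counted as not recovered, against 92% with Kaplan-Meier. With no true effect, the false-positive rate is about 15% (lost = not recovered), 9% (dropped) and 5% (Kaplan-Meier).

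**6. Slower loss.** With the same 10%/30% spread over 14 days, the day-7 odds ratios are 1.78 and 2.21. At day 12 they are 1.70 and 2.79 against a true value of about 2.44.

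**7. Where Kaplan-Meier fails.**

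- Censoring on day 14 (the study-end reading), with 20% loss over 14 days, gives 0.377/0.549 at day 7, exactly the figures with lost counted as not recovered.
- Deaths censored at last contact (assumed 5% v 2%) give 0.582/0.773 at day 12 against a true 0.572/0.769.
- If slow recoverers are lost more often, day 12 reads 0.611/0.796 against a true 0.583/0.774.

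**The case against.** The strongest reply is that the censoring sentence follows the Kaplan-Meier, Cox and log-rank sentences and was meant for those alone. What remains is an unstated rule for a missing binary status, which a statistical analysis plan commonly supplies. The number of days to recovery is in any case already analysed by survival methods. This reply carries weight: the odds ratios sit beside a sound type of analysis and do not replace it. It does not remove the point. The protocol itself fixes a method that cannot carry the incomplete patients it expects, and the censoring rule is faulty for the survival analysis as well.

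A reader might infer that the day-7 and day-12 odds ratios will be distorted. The documents do not support that. With equal, unrelated loss, dropping patients of unknown status leaves the odds ratio near 2.07, and counting them as not recovered moves it only to about 1.95. Dropping everyone who left early, recovered or not, is also unbiased when loss is unrelated to recovery. No loss by arm is given, and the 20% covers refusals too, so loss after randomisation may be smaller.

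A reader might also infer that Kaplan-Meier cures the problem at no cost. It does not, as step 7 of the working shows. Adverse-effect withdrawal, the likeliest source of unequal loss, may itself be related to recovery.

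**Conclusion.** The point holds as a mismatch of stated methods that should be corrected. The logistic analysis of early and late recovery cannot follow the stated censoring, and the single censoring rule is wrong for deaths on one reading and for lost patients on the other.

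The size depends on loss that the protocol does not specify. It is small if loss is equal. It is material if loss is clearly unequal: a day-7 odds ratio between about 1.6 and 2.4 against 2.07 under an assumed 10%/30% split within 7 days, and less if loss is spread over 14 days. All these figures rest on a constant recovery hazard, loss unrelated to recovery, and 0.40 and 0.58 as day-7 rates.

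**What to change.** - Replace the logistic sentence: report the proportions recovered by day 7 and day 12, and their difference with 95% CI, from the Kaplan-Meier analysis already planned for duration of recovery, in all randomised patients.
- Replace the single censoring rule. Censor lost patients on their own last assessment day. Keep deaths as not recovered through day 12. Analyse patients who stop drug for an adverse effect with whatever follow-up they have, and do not censor them for stopping.
- Reconcile the wording that takes patients with adverse effects out of the study with the intention-to-treat statement.
- Keep the logistic odds ratio, with lost patients counted as not recovered, as a sensitivity analysis for informative loss. Edit to match the sentence that adjusts the crude odds ratio in a Cox model.

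This takes a few sentences and no new data, since clinical status is already assessed daily. The statistical price is a standard error for the day-7 difference of about 0.051 to 0.052 against 0.049 with full follow-up (power 92% to 94% against 95% at 200 per group, equal 20% loss), reliance on loss being unrelated to recovery, and no covariate adjustment in the Kaplan-Meier estimate.

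### Odds ratios for recovery are to be adjusted in a Cox model, and PCR persistence is given a hazard ratio with no event defined

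*Protocol*

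**What the plan says.** **Recovery.** The Primary Outcome Measure section has two components, early improvement (time frame 7 days) and late recovery (12 days). For these, the Data analysis section says: "Odds ratio will be formulated from linear logistic regression for early and late clinical recovery". Shortly afterwards it adds: "Crude odds ratio will be adjusted in cox proportional hazard ratio model".

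**PCR persistence.** The same section says: "Hazard ratio will be formulated from the cox regression analysis for severity conversion and persistence of the positivity". The second secondary outcome is defined as "Percentage of Covid-19 Patients repeatedly become positive for RT-PCR for Covid-19", with a 14-day time frame. Under Data collection technique, "RT-PCR will be done at day-0, Day 5, day 7 and day 14". The inclusion criteria require "COVID-19 infection, confirmed by polymerase chain reaction (PCR) test within 3 days from enrollment", so patients enter with confirmed infection.

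**Censoring.** The only rule is: "Participants who were lost to follow up, died, discontinue drugs due to adverse effect will censored on the last study day". A patient whose swab turns negative is not on that list.

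**The concern.** There are two mismatches between an outcome and the model assigned to it.

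The first concerns recovery. An odds ratio compares the odds of having recovered by a given day. A Cox hazard ratio compares rates of recovery over time. Moving from one to the other is a change of parameter and not an adjustment. A reader who sees a crude odds ratio beside a smaller figure labelled as adjusted would put the difference down to baseline imbalance. This touches the components of the primary outcome.

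The second concerns PCR. Cox regression needs an event and a time at which it happens. Patients start positive, so the event that can occur is clearance, and persistence means that it has not occurred. The protocol lists persistence as a percentage and does not say what counts as the event, when it is timed, or what happens to a patient who clears. Different analysts could follow the same sentence and report different hazard ratios from the same data. This is the only virological outcome, and the general objective claims a microbiological as well as a clinical benefit.

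**Working it through.** **The protocol's own figure.** Its only computed figure is the sample size. With arcsin√0.40 = 0.6847 and arcsin√0.58 = 0.8657, N = ½ × (2.805 / 0.1810)² = 120.05, rounded up to 121. It reproduces. It does not bear on this point, and the protocol gives no figure for the recovery or PCR analyses.

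**1. Odds ratio against hazard ratio for recovery.**
Inputs: response rates of 0.40 (standard care) and 0.58 (new treatment) from the sample-size paragraph. The assumptions are that these are proportions recovered by a fixed day and that hazards are proportional.
- Odds ratio = (0.58/0.42) / (0.40/0.60) = 1.381 / 0.667 = 2.07.
- Hazard ratio = ln(0.42) / ln(0.60) = 0.868 / 0.511 = 1.70.

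With no confounding at all, the reported effect moves from 2.07 to 1.70.

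**2. PCR persistence, everyone kept to day 14.**
Inputs: 200 per arm (protocol); the persistence rates are assumed, since the protocol gives none. With one common time and Breslow ties, the Cox estimate equals the risk ratio. Its log variance is 1/d₁ + 1/d₀, where d₁ and d₀ are the numbers still positive, while the log risk ratio has variance 1/d₁ − 1/n + 1/d₀ − 1/n. If a proportion q is positive in both arms, the standard error is too large by the factor 1/√(1−q): 1.05 at q = 10% and 1.29 at q = 40%.

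| Assumed positive, placebo v active | Risk ratio (SE of log) | Cox, Breslow (SE of log) | Cox, Efron | Odds ratio |
|---|---|---|---|---|
| 10% v 5% | 0.50 (0.374) | 0.50 (0.387) | 0.487 | 0.474 |
| 20% v 10% | 0.50 (0.255) | 0.50 (0.274) | 0.473 | 0.444 |
| 40% v 20% | 0.50 (0.166) | 0.50 (0.194) | 0.441 | 0.375 |
| 20% v 8% | 0.40 (0.278) | 0.40 (0.296) | 0.375 | 0.348 |

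In the last row the 95% interval is 0.22-0.71 from Cox and 0.23-0.69 for the risk ratio, so the standard error is 0.296/0.278 = 1.06 times too large.

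**3. PCR persistence, patients censored at first negative swab.**
The protocol does not state this coding; it is one that the sentence leaves open. All events fall on day 14, so the hazard ratio compares day-14 positivity only among those still positive after day 7. Both clearance patterns are assumed.
- Pattern A, first negative at day 5/7/14 and persistent: placebo 20/40/100/40, active 40/60/80/20. Still positive after day 7: 140 and 100. HR = (20/100) / (40/140) = 0.70 (p = 0.19). Risk ratio = 20/40 = 0.50.
- Pattern B: placebo 60/40/60/40, active 100/60/24/16. Still positive after day 7: 100 and 40. HR = (16/40) / (40/100) = 1.00 (0.56-1.79). Risk ratio = 16/40 = 0.40 (0.23-0.69).

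**4. Clearance as the event.** In pattern A, Cox regression on time to first negative swab gives HR 1.39 (SE of log 0.109). Benefit is now above 1, so even the direction of a favourable hazard ratio is not fixed until the event is named.

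**The case against.** The strongest defence is that this is loose wording, and parts of that defence stand.

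- **Cox on duration of positivity is ordinary.** The protocol uses the idea of persisting for a duration when it defines late recovery, so persistence of positivity could mean time to negative. That is a fair reading, and Cox need not give a wrong answer. But the listed measure is a percentage, and the event is nowhere named.
- **Keeping everyone to day 14 does little harm.** This also stands. Direction and point estimate are preserved with Breslow ties, and the error is conservative.
- **The odds-ratio sentence may only mean crude odds ratios plus separately adjusted hazard ratios.** Possibly, but it says that the odds ratio itself is adjusted in the Cox model. A correct logistic adjustment can also shift an odds ratio without confounding, yet what it returns is still an odds ratio.

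A reader might infer that the plan as written would report a real effect on clearance as a hazard ratio of 1. The documents do not support that. It needs censoring at the first negative swab, which the censoring rule does not include. It also needs the equal 40% day-14 positivity among those still positive (16/40 and 40/100) that pattern B happens to have; pattern A gives 0.70. Nor does the text say that the outcome is status on day 14 alone: it speaks of repeated positivity within 14 days. The 29% upper figure for the standard error needs 40% positive in both arms, which the documents do not give.

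**Conclusion.** Both mismatches are in the protocol's own text and hold in limited form.

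The odds-ratio sentence is wrong as written and reaches both components of the primary outcome. With the protocol's rates the change of parameter alone is 2.07 to about 1.70, given proportional hazards and those rates read as recovery proportions.

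For PCR persistence, a percentage outcome is paired with a hazard ratio for which no event is defined. The consequence depends on a coding choice left open. It ranges from a standard error about 5-29% too large (10-40% positive assumed, Breslow ties) to attenuation of the effect if negatives were censored when they clear (0.70 against 0.50, or 1.00 against 0.40). All persistence and clearance rates here are assumptions, and the attenuated figures illustrate what could happen without forecasting it.

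The point does not extend to severity conversion, which is a change of state that can have an event time. It does not affect the Kaplan-Meier and log-rank comparison of time to recovery. The change should be made.

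**What to change.** Replace the two sentences in the Data analysis section with:

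1. Adjusted odds ratios for early and late clinical recovery will come from multivariable logistic regression; adjusted hazard ratios will come from Cox regression. Each will be labelled as what it is.
2. RT-PCR persistence by day 14 will be compared as a risk ratio, risk difference or logistic odds ratio. If a hazard ratio is wanted, the event is the first negative RT-PCR, in an analysis that allows for swabs after entry only on days 5, 7 and 14 (for example, interval-censored).

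Alongside the second sentence, state which swab pattern counts as persistent, since the outcome speaks of repeated positivity. The choice of covariates and the handling of missing swabs can be left to the statistical analysis plan.

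The cost is two sentences. No new data are needed: the swabs are already scheduled, and the protocol's summary already names binary logistic regression.
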